#### **4.6 LOST TO FOLLOW-UP**

Subjects who miss at least two consecutive visits, as defined by the visit windows and cannot be contacted, may be considered lost to follow-up. All follow-up attempts will be documented and kept with the subject's source documentation, and the applicable eCRFs will be completed.

Subjects that voluntarily withdraw consent after implantation with the HMIOL will be considered Lost to Follow-Up and an Exit Form will be completed.

#### **4.7 STUDY COMPLETION**

ClarVista will notify the Investigators when to contact the IRB / EC to announce study completion at the site.

#### 4.7.1 EARLY STUDY TERMINATION

ClarVista has the right to terminate this study at any time. Reasons for terminating the study may include, but are not limited to, the following:

- The incidence or severity of adverse events in this or any ongoing studies involving the same technology (if applicable), indicates a potential health hazard to subjects
- Subject enrollment is unsatisfactory
- Data recording is inaccurate or incomplete.

In the event of premature study termination, appropriate notification will be given to the Investigators, IRB / ECs, and regulatory bodies as applicable. In addition, ClarVista (or designee) will instruct all Investigators to discontinue dispensing study materials or treatments, will ensure all subjects complete appropriate follow-up, and will arrange study closeout visits at each site as appropriate.

### 4.8 CONCOMITANT THERAPIES

#### 4.8.1 CONCOMITANT MEDICATION

Concomitant medications are any prescription drugs used by a subject until conclusion of study participation. Any medication the Investigator deems in the best interest of the subject, is acceptable to prescribe or administer. However, any and all are to be recorded in both the Concomitant Medication source document and eCRF as well as the reason for use (indication). An AE is to be reported and/or recorded as appropriate (see Section 6.0).

#### 4.8.2 CONCOMITANT PROCEDURES

A concomitant procedure is any invasive or non-invasive ocular or peri-ocular procedure that takes place during study participation and will be captured in both the Concomitant Procedure Source Document and eCRF. The following are examples of two such procedures:

- Any PO surgical adjustments (i.e. corneal refractive surgery, lens exchange, etc.)
- Neodymium: Yttrium-aluminum-garnet (Nd:YAG) procedure to treat Posterior Capsule Opacification (PCO), if necessary. This will be listed as "Nd:YAG Capsulotomy."

**Note:** Any Nd:YAG capsulotomy procedures prior to exit will be performed only in response to spontaneous subject complaints (i.e. not solicited by study personnel) of reduced Visual Acuity (VA) or glare that affects functional vision, which is associated with PCO or striae, and captured on the eCRF in SLE findings.

An AE is to be reported and/or recorded as appropriate (see Section 6.0). Any procedure reported in the Concomitant Procedure eCRF must have a corresponding Indication listed in either the Ocular History or AE eCRF (Only exception: PCO – See Section 6.1 for further details).

### 4.9 PROTOCOL DEVIATIONS

All protocol deviations, the date of deviation, and reason will be documented in the Source Document and eCRF. All deviations will be categorized as either major or minor in the following manner:

**Major:**

- Deviations impacting subject safety (e.g. eligibility, etc)
- Deviations impacting subject rights (e.g. consent, etc)
- Deviations impacting data integrity (e.g. instrumentation, masking, etc)

**Minor:**

[figure not shown]
- All other deviations (e.g. out of window visits, missed data point, etc.)

All major deviations must be reported by the Investigator to the Sponsor and IRB/EC immediately. Subject assessments will continue per protocol for the duration of planned participation unless the deviations put the subject at risk or the subject's condition requires that he/she be discontinued from the study.

## 5.0 STUDY MATERIALS

### 5.1 DESCRIPTION OF TEST ARTICLE

The HARMONI™ Modular Intraocular Lens (HMIOL) System is device designed to allow safe exchange or adjustment of an IOL optic after implantation.

#### 5.1.1 INSTRUCTIONS FOR USE

Refer to the Surgical Guide for all use and administration details.

#### 5.2 PACKAGING AND LABELING

All packaging and labeling will be consistent with the current study design. The labeling will include at a minimum, the following:

- Sponsor name and address
- "For Single Use Only" statement (or equivalent symbol)
- Sterility symbol
- Storage temperature range requirements or equivalent (e.g. "Store at room temperature.")
- Expiration date
- Power designation
- Unique serial number
- Model number

#### 5.3 ACCOUNTABILITY

The Investigator is responsible for keeping accurate accountability records of the number of study lenses received, dispensed, and returned to Sponsor. The study lenses must be stored under the appropriate conditions in a secure area and are to be implanted only in subjects enrolled in the study, in accordance with the conditions specified in this protocol.

All accountability records will include the following:

- Model and serial numbers
- Receipt date
- Quantities received
- Initials (attributability) of site personnel who received, dispensed, or returned study lenses
- Date of use
- Subject and eye treated with the study lens (by Subject ID and Initials only)
- Date returned to Sponsor
- Defective or damaged study devices

Periodically throughout the study and/or upon completion, the Sponsor (or designee) will review and verify the Investigator's accountability records. Following verification, and as directed by the Sponsor, all unused and explanted products must be returned to the Sponsor.

**Note:** In addition, any study lenses or components deemed defective, damaged, malfunctioning, or explanted must be retained by the site and returned to the Sponsor for evaluation. Under no circumstances are any components to be discarded or otherwise disposed of. If there is any question as to the applicability of this directive, consult the Protocol Contacts page of this protocol and discuss the situation with a Sponsor representative.

## 5.4 OTHER MATERIALS

Additional materials can be provided to sites for the duration of the study on an as-needed basis and may include:

- ETDRS light box, glare source, and charts to perform the standardized VA assessments described in the Manual of Procedures
- Medicel injectors (for study lens injection only)
- IOL micro-incision cutter and forceps
- Konan Specular Microscope
- Slit lamp camera

## 6.0 ADVERSE EVENTS

Safety assessments include adverse events/serious adverse events, and adverse device events. The reporting time period is from the time of consent through the last study visit (3 Month Visit post cataract extraction).

### 6.1 DEFINITIONS

#### 6.1.1 ADVERSE EVENT (AE)

An AE is any untoward medical event in a subject that does not necessarily have a causal relationship to the study device or protocol. AEs include Adverse Device Effects (ADEs). Conditions or diseases that are pre-existing and/or chronic but stable should not be recorded on AE pages of the eCRF. Similarly, changes in a pre-existing and/or chronic condition of disease that are consistent with natural disease progression are NOT adverse events and also should not be recorded on the AE pages of the eCRF.

Refer to Section 6.3.1 for instructions regarding events that require expedited reporting to the Sponsor and IRB/EC.

Experience with cataract surgery and the implantation of IOLs has shown that some conditions can be considered normal or expected events following these procedures. The following may be considered normal or expected events after cataract surgery and only need to be reported as AEs as specified here:

- Iritis (cell / flare) – if treated
- Persistent Corneal Stroma Edema (if present at 1 Month)
- Increased IOP only if medical/surgical intervention is required (i.e. medication, paracentesis manipulation)
- VA decrease of 10 or more letters (2 lines) from any previous visit not secondary to any underlying condition
- Any expected post-operative ocular event requiring a change in standard postoperative medication regimen

**Note:** PCO is not to be reported as an AE, as per ISO 11979-7:2014.

Particular attention should be paid to ensure timely and accurate reporting of any of the following cataract surgery related events:

- Endophthalmitis
- Capsular injury
- Vitreous loss
- Macular edema
- Retinal detachment
- Lens dislocation
- Moderate to severe corneal edema
- Pupillary block / angle closure
- Hypopyon or hyphema

#### 6.1.2 ADVERSE DEVICE EFFECT (ADE)

An ADE is any untoward or unintended effect, event, or response surrounding and with a causal relationship with the use of a medical device. This definition may include any event resulting from insufficiencies or inadequacies in the instructions for use or the deployment of the device or other device malfunctions. This definition includes any event that is a result of a user error and any event that affects a user of the device (i.e. caregiver, bystander, etc.).

#### 6.1.3 UNANTICIPATED ADVERSE DEVICE EFFECT (UADE)

A UADE is any ADE, which is unanticipated and poses a risk to health or safety, or any life-threatening problem or death caused by or associated with a device, if that effect, problem, or death was not previously identified in nature, severity or degree of incidence (see Investigator Brochure [IB]). UADEs also include any unanticipated sight-threatening events and any other unanticipated serious problem associated with a device that relates to the rights, safety, or welfare of subjects.

#### 6.1.4 DEVICE DEFICIENCIES (DD)

A Device Deficiency (DD) is a failure of the device to meet its performance specifications or expectations, or otherwise not perform as intended. This can include either a malfunction or damage to the device or any part thereof, regardless of the source of malfunction or damage, including user error, and regardless of the presence of injury (or lack thereof) to subject, user, or bystander.

### 6.2 AE EVALUATION

AEs experienced in this study may be associated with the study device (i.e. ADE) or the study protocol as demonstrated in the following non-exhaustive list of examples:

#### Study Device (ADE)

- IOL dislocation
- Explant due to haptic break/damage
- Explant due to base and/or optic damage

**Study Protocol**

- Allergic reaction to dilating drops
- Lens remnants following surgery
- Capsular tear during surgery to implant study device

**6.2.1 EVALUATION**

All AEs will be evaluated for and by the following criteria:

- Classification (SAE, AE, ADE or combination)
- Diagnosis (or description if ADE)
- Severity
- Relationship (Causality) to study protocol or device
- Outcome
- Treatment or action taken

**6.2.1.1 CLASSIFICATION**

When evaluating AEs, the Investigator must determine if the event is serious using the following guidelines:

**A Serious Adverse Event (SAE)** is any AE (ocular or non-ocular) that:

- results in death
- results in serious injury, defined as:
  - ◆ life-threatening
  - ◆ permanent impairment of a body function (e.g. blindness) or structure
  - ◆ necessitates medical or surgical intervention to prevent permanent impairment of a body function or permanent damage to a body structure, or
  - ◆ results in a potentially sight-threatening condition
- is a malfunction that might cause or contribute to a serious injury or death if it were to recur
- requires in-patient hospitalization or prolongation of existing hospitalization\*, or
- leads to fetal distress, fetal health, a congenital abnormality, or birth defect

\*Hospitalization is a criterion for assessment of seriousness. Hospitalization in the absence of a medical AE is not in itself an AE. For example, the following reports of hospitalization without a medical AE should not be considered either serious or an AE:

- admission for treatment of a pre-existing condition not associated with the development of a new AE or with worsening of the pre-existing condition (e.g. for work-up of persistent pretreatment lab abnormality)
- social admission (e.g. subject has no place to sleep)
- administrative admission (e.g. for yearly physical exam)
- optional admission not associated with a worsening of a pre-existing condition (e.g. elective cosmetic surgery or elective surgery for pre-existing repair of the Achilles tendon [which had not worsened while on study])

- hospitalization for admission without a medical AE

*NOTE: For the purposes of this protocol, any UADE will be considered an SAE.*

#### **6.2.1.2           DIAGNOSIS OR DESCRIPTION**

In all instances, it is preferable to report all AEs and SAEs by diagnosis rather than a sign or symptom if possible. This may necessitate the revision of a previously reported AE or SAE as more information is obtained.

#### **6.2.1.3           SEVERITY**

When evaluating AEs, the Investigator must determine the severity of symptoms using the following guidelines:

- Mild: Subject awareness of a sign or symptom that is easily tolerated, requires no treatment, and does not interfere with the subject's daily activities
- Moderate: Subject awareness of a sign or symptom which may be a low level of concern to the subject and may interfere with daily activities, but can be relieved by simple therapeutic care
- Severe: A sign or symptom that interrupts the subject's daily activity and requires systemic therapy or other treatment

#### **6.2.1.4           RELATIONSHIP (CAUSALITY) TO STUDY DEVICE OR STUDY PROTOCOL**

When evaluating AEs, the Investigator must evaluate the relationship of the event to the study device and study protocol, using the following guidelines:

- Not Related: AEs which are clearly and incontrovertibly due to causes other than the study device or study protocol (e.g. concomitant disease, etc)
- Related: AEs which are felt with a reasonable degree of certainty to be related to the study device or study protocol
- Unknown: Adverse events for which a connection with the study device or study protocol cannot be ruled-out with certainty, or not enough information is available to assess the relationship

#### **6.2.1.5           OUTCOME**

The clinical outcome of an AE will be categorized as follows:

- Resolved without sequelae
- Resolved with sequelae (specify)
- Ongoing (i.e. continuing at time of study discontinuation)
- Death

#### **6.2.1.6           TREATMENT OR ACTION TAKEN**

Treatment or Action Taken will be categorized as follows:

- None

- Medical Intervention (specify on Concomitant Medication Source and eCRF)
- Surgical Intervention (specify on Concomitant Procedure Source and eCRF)
- Other (specify)

### 6.3 REPORTING

#### 6.3.1 ON-SITE EXPEDITED REPORTING

The Investigator is obligated to report the following to the Sponsor within 24 hours of becoming aware of the event to ensure the safety of all participants in the study and to meet regulatory reporting requirements:

- All SAEs, regardless of relationship to study device or study protocol utilizing the SAE/ADE Report Form
- All AEs determined to be related to the study device (ADEs or UADEs) utilizing the SAE/ADE Report Form
- All HMIOL explants (consult Medical Monitor listed on Protocol Contacts page prior to explant, if possible)
- All Device Deficiencies (DD) utilizing the DD Report Form

*Refer to the Protocol Contacts page for appropriate Sponsor contact to report the above events.*

**NOTE: Any explanted HMIOL devices, exchanged HMIOL optics, or any components of the HMIOL System presenting a deficiency or malfunction are to be retained by the site until collected by the Sponsor. Under no circumstances are they to be destroyed or otherwise discarded.**

When reporting these events to the Sponsor, the site should forward any supporting documents along with the appropriate reporting form and complete the corresponding eCRF, if applicable. Sites must also report applicable events to the reviewing IRB/EC per its established reporting procedures.

#### 6.3.2 OFF-SITE SAE REPORTING

As a multicenter clinical trial, the Investigators may receive "off-site" reports (e.g. an SAE Report). These are Sponsor reports of SAEs which occurred at other sites for the same trial, or in different trials using the same test article, that met the criteria for reporting. These should be reported to the reviewing IRB per their established reporting procedures.

#### 6.3.3 REPORTING OF COMPLAINTS FOR ANCILLARY MARKETED PRODUCTS

Any complaints, malfunctions or similar events related to ancillary marketed products used in this study should be reported by the Investigators in accordance with the reference information provided on the associated commercial packaging.

#### 6.3.4 ADVERSE EVENTS AND SERIOUS ADVERSE EVENTS AT SUBJECT EXIT

Ongoing SAEs and ADEs will be followed until resolution or no further change in the condition is expected. Non-serious AEs that are ongoing at study exit visit or upon discontinuation from the study will be followed per the Investigator's standard of care. Documentation in the eCRF of this follow-up is not required although subject care should continue as appropriate.

### 6.4 SAFETY MONITORING AND REVIEW

All reported AEs will be reviewed on a weekly basis and assessed for trending and causality to study device or procedure. ADEs, UADEs, DDs, and SAEs will be reviewed upon receipt of expedited reporting (Section 6.3.1). Any unexpected trends or events will necessitate careful review and assessment of any change in the risks associated with participation or study continuation.

If an event occurs affecting a subject's risk of participation, Off-Site Reporting (Section 6.3.2) will be utilized to update sites and the IRB(s) / EC(s). If the safety profile of the event provides for the continuation of the study, Informed Consent Forms will be revised as necessary to ensure subjects' consent to continue participation given the known revised risks.

As outlined in Section 4.7.1, the Sponsor reserves the right to discontinue enrollment at any time.

## 7.0 CLINICAL ENDPOINTS

### 7.1 SAFETY ENDPOINTS

Safety will be evaluated by assessing the following:

- Percent change in ECC at the 3 Month Visit compared to Preoperative Visit
- Preservation of BCDVA
- SSI
- AE rates as compared to ISO 11979-7:2014 Annex B SPE tables
- Device deficiencies

[figure not shown]
### 7.2 EFFECTIVENESS ENDPOINTS

- 1 and 3 months MRCYL for eyes implanted with HMTIOL
- 1 and 3 months MRCYL prediction error for eyes implanted with HMTIOL
- 1 and 3 months MRCYL prediction error for eyes implanted with HMTIOL per vector analyses
- 1 and 3 months SEQ prediction error
- UCDVA by study visit
  - Percent of eyes that achieve
    - 20/20 or better
    - 20/25 or better
    - 20/32 or better
    - 20/40 or better
    - Worse than 20/40
- BCDVA by study visit
  - Percent of eyes that achieve
    - 20/20 or better
    - 20/25 or better
    - 20/32 or better
    - 20/40 or better
    - Worse than 20/40

- Rotational of IOL meridian at 1 day, 1 week, 1 and 3 months
  - Percent of eyes with rotation < 10°
  - Percent of eyes with rotation < 20°
  - Percent of eyes with rotation < 30°
- Reduction in cylinder power of the eye implanted with HMTIOL (absolute preoperative magnitude of corneal cylinder (K) minus the absolute postoperative magnitude of MRCYL at the corneal plane)
- Percentage reduction in cylindrical power of the eye implanted with HMTIOL (absolute preoperative magnitude of corneal cylinder (K) minus the absolute postoperative magnitude of MRCYL at the corneal plane, expressed as a percentage of the absolute preoperative magnitude of total corneal cylinder (K)).

## 8.0 STATISTICAL METHODS

This is a feasibility study to evaluate the safety and effectiveness of HTMIOL in subjects with primary cataract surgery and subjects with HTMIOL intra-operative optic exchange. In general, the analyses will be provided based on available data. The mean, standard deviation, minimum, and maximum will be prepared for the continuous clinical parameters, and counts and percentages will be presented for the categorical outcomes.

This is a feasibility study and no adjustment will be performed for the multiplicity.

## 8.2 ANALYSES POPULATIONS

Subjects that are screened but disqualified based on the preoperative and intra-operative eligibility criteria will be excluded from the safety and effectiveness data analyses. However, their reasons for the screen failure will be summarized. The analyses populations are defined below.

### 8.2.1 SAFETY POPULATION

The **Safety Population** includes eyes with attempted study lens (HMTIOL or HMIOL) implantation, (successful or aborted after contact with the eye). The intraoperative and postoperative AEs and DDs will be summarized based on the safety population.

### 8.2.2 IMPLANTED-EYE POPULATION

The **Implanted-Eye** Population consists of eyes with successful HMTIOL or HMIOL implantations during surgeries. Since it is important to evaluate HMTIOL or HMIOL's effect on the study eyes, the assessment of ECC, slit lamp examination, intraoperative pressure (IOP), and dilated fundus examination (DFE) will be based on the implanted-eye population. It should be noted that the ECL comparison between Cohort 1 and Cohort 2 of this study will be based on the subjects with successful implants in both eyes and have available ECL at 3 months.

Additionally, the UCDVA, BCDVA, prediction error, and meridian rotation will be evaluated based on the implanted-eye population.

### 8.2.3 PER PROTOCOL POPULATION

The **Per Protocol (PP)** Population contains eyes with successful HMTIOL or HMIOL implantations during surgeries and do not have major protocol deviation (such as improperly enrolled in the study or lens power calculation errors) and will be considered the primary population for effectiveness outcomes. The effectiveness outcomes (UCDVA, BCDVA, and prediction error) will be evaluated based on the per protocol population.

The protocol deviations will be determined reviewed by ClarVista clinical personnel prior to analysis.

### 8.2.4 BEST-CASE POPULATION

The **Best Case** population is the PP population with all of the following characteristics:

- No clinically significant preoperative ocular pathology in the study eye, including any of the following present at the preoperative visit
  - Pseudoexfoliation
  - Glaucoma
  - Uveitis

- Retinal detachment
- Diabetic retinopathy
- Macular degeneration
- Amblyopia
- Others as specified by unmasked sponsor clinical personnel after a review of the adverse events present at the preoperative visit

- No macular degeneration detected at any time in the study eye
- No previous surgery for the correction of refractive errors in the study eye

The purpose of the Best Case population is to evaluate BCDVA as described in ISO 11979-7:2014.

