5.9. Effectiveness Analyses

All endpoints listed above will be summarized by study visit and cohort as described in section 5.1 based on the Implanted Eye Population. BCDVA will also be summarized based on the Best-case population as suggested by ISO.

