7.1.3. PER PROTOCOL POPULATION

The Per Protocol (PP) Population contains eyes with successful HMTIOL or HMIOL implantations during surgeries and do not have major protocol deviation (such as improperly enrolled in the study or lens power calculation errors) and will be considered the primary population for effectiveness outcomes. The effectiveness outcomes (UCDVA, BCDVA, and prediction error) will be evaluated based on the per protocol population.

The protocol deviations will be reviewed by ClarVista clinical personnel prior to analysis.

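### Unmasked sponsor staff may add preoperative exclusions to the Best Case set, with no cut-off date and no bar on knowing postoperative acuity

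*Protocol*

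**What the plan says.** Best Case is the Per Protocol population restricted to eyes without clinically significant preoperative pathology. Protocol 8.2.4 names seven conditions and then adds "Others as specified by unmasked sponsor clinical personnel after a review of the adverse events present at the preoperative visit". A separate criterion reads "No macular degeneration detected at any time in the study eye", so one named condition can already be found after surgery. The stated use is narrow: "The purpose of the Best Case population is to evaluate BCDVA as described in ISO 11979-7:2014". SAP 5.9 agrees: "BCDVA will also be summarized based on the Best-case population as suggested by ISO".

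For the Per Protocol population, Protocol 8.2.3 removes eyes with a major deviation, "such as improperly enrolled in the study or lens power calculation errors". On who decides, it says "The protocol deviations will be determined reviewed by ClarVista clinical personnel prior to analysis"; SAP 7.1.3 says "The protocol deviations will be reviewed by ClarVista clinical personnel prior to analysis". Both documents give this population a leading role; in the SAP's words it "will be considered the primary population for effectiveness outcomes".

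**The concern.** The Best Case wording is a positive rule, not a silence. It names the deciders, describes them as unmasked, leaves the category open and sets no point at which it closes. Tying additions to preoperative findings limits what can be added, but not the order of reasoning: someone who knows which eyes finished worse than 20/40 can look harder at the baseline records of those eyes. Exclusion that depends on outcome in this way can only flatter the acuity result.

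The Per Protocol rule has a milder form of the same weakness. Reviewing deviations before the analysis fixes the order of review and tabulation. It does not keep the reviewer from eye-level acuity or refraction. A lens power calculation error is the kind of deviation that may first be suspected because of an unexpected refraction (an inference; the documents do not say so), and refraction is what the prediction-error endpoint measures.

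**Working it through.** The point is mainly textual, so the relevant passages come first, followed by a small calculation of leverage.

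**1. Does any other text supply the missing safeguard?**

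- Protocol 9.1.1 promises masking as far as possible, without linking it to population decisions.
- SAP 8 withholds accruing results from investigators and subjects. Sponsor staff are not mentioned.
- Protocol 6.4 has adverse events reviewed weekly, and Protocol 6.1.1 makes a loss of 10 or more letters without an underlying cause reportable. Some eye-level acuity information therefore circulates during the study; the reviewer is not named.
- Protocol 8.2.3 and SAP 7.1.3 time the deviation review but set no condition on what the reviewer may know.

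None of these closes the gap.

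**2. How much room does the open item have?**

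Protocol 3.2.2 already bars, in either eye, pseudoexfoliation (criterion 7), chronic uveitis (8), uncontrolled glaucoma (10), prior corneal or intraocular surgery (1 and 5), and retinal detachment, diabetic retinopathy, macular degeneration or amblyopia that could limit the visual prognosis (6). An eye enrolled in breach of eligibility is a major deviation under Protocol 4.9 and leaves at the Per Protocol step. Among the named conditions, this leaves mainly controlled glaucoma and macular degeneration found later. Two things follow: few eyes can be affected, and the open item is one of the few routes by which Best Case can differ from Per Protocol.

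The record to be searched is also unclear. The rule refers to adverse events present preoperatively, yet Protocol 6.1.1 keeps stable pre-existing conditions off the adverse event pages.

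**3. Leverage of one exclusion.**

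Inputs: up to 32 subjects with one eye in each cohort (Protocol 3.1; SAP 6), and 25 evaluable eyes per cohort (SAP 6, planned for the endothelial cell comparison). The plan's own inflation reproduces: 25 / (1 − 0.20) = 31.25, rounded up to 32. The number of eyes worse than 20/40 is not given; one to three is an assumption.

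With n eyes and s at 20/40 or better, removing one failing eye changes the rate by s/(n − 1) − s/n = s / [n(n − 1)].

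| n | Failures (assumed) | None removed | One removed | Two removed |
|---|---|---|---|---|
| 25 | 1 | 24/25 = 96.0% | 24/24 = 100% | – |
| 25 | 2 | 23/25 = 92.0% | 23/24 = 95.8% | 23/23 = 100% |
| 25 | 3 | 22/25 = 88.0% | 22/24 = 91.7% | 22/23 = 95.7% |
| 32 | 1 | 31/32 = 96.9% | 31/31 = 100% | – |
| 32 | 2 | 30/32 = 93.8% | 30/31 = 96.8% | 30/30 = 100% |
| 32 | 3 | 29/32 = 90.6% | 29/31 = 93.5% | 29/30 = 96.7% |

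The first removal adds between 29/(32 × 31) = 2.9 points and 24/(25 × 24) = 4.0 points. No figure in the documents changes.

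**The case against.** The strongest reply is that the discretion is narrow and its result visible. Staff cannot invent reasons: an added condition must be an instance of clinically significant preoperative pathology, and eligibility has removed most such eyes. Reaching 100% in the table would require every failing eye to have a qualifying finding. The Implanted-Eye tables keep every excluded eye, so a gap between the two would be seen. All of this stands, and it is why the point is minor.

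On Per Protocol, Protocol 4.9 requires each deviation to be dated, explained and classed as major or minor by written definitions, with major ones reported at once to the sponsor and the ethics body. The record therefore starts at the site and is partly external. That stands too, though one definition, impact on data integrity, is broad, and under Appendix A the sponsor approves the power calculation whose errors it would later judge. SAP 5.9 and 5.9.3 summarise effectiveness on the Implanted-Eye population, and SAP 2 says the SAP's analyses supersede those of the Investigational Plan. This blunts the effect of Per Protocol exclusions. It also conflicts with the primary label in SAP 7.1.3, a separate inconsistency to reconcile.

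Three stronger readings are tempting and not supported:

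- That Best Case exclusions raise the refractive results. Best Case is used for BCDVA only.
- That a formal ISO comparison of BCDVA is compromised. The readable text gives no acuity pass mark or test on this population. The explicit comparison with ISO rates in SAP 5.5 concerns adverse events, which are summarised on the Safety population. Parts of the BCDVA sections are redacted, so such a comparison can be neither confirmed nor assumed.
- That unmasked means the staff have reviewed postoperative acuity. The word does not say so. The point is only that nothing prevents it.

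**Conclusion.** The point holds in limited form and is a desirable clarification, not a flaw that undermines the study. The Best Case rule permits additions by staff who may know the outcome, with no lock point, and the limit to preoperative findings reduces the scope for selective searching without removing it. One such exclusion would move the 20/40-or-better rate by about 3 to 4 points. That size rests on assumed failure counts and on 25 to 32 eyes per cohort; Best Case is a subset of Per Protocol, so its denominators could be smaller and the step larger. The Per Protocol part is weaker, because deviations are documented as they occur and reviewed before analysis. What remains there is the freedom to make calls such as lens power calculation error after seeing eye-level refraction. Nothing in the documents suggests misuse, and sample size is unaffected.

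**What to change.** Either restrict Best Case exclusions to the conditions already named in Protocol 8.2.4, or add to the SAP that any other condition, and every major-deviation call, is decided from preoperative and surgical records only and signed and dated before 3-month acuity and refraction are tabulated. A deviation that arises after surgery should be judged from the deviation record without the acuity or refraction values. In either case, list each eye excluded from Per Protocol or Best Case with its reason. It would also help to name the preoperative record to be reviewed, such as the baseline examination and ocular history, since the adverse event pages will not hold stable conditions.

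The cost is one or two sentences in the SAP and a dated sign-off sheet, with no new data, visits or staff. The downside is slightly less freedom to refine the populations late.
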